## 8.2 Use of Electronic Medical Record

The electronic medical record (Epic) will be used to extract the following social and medical history. Demographic data (e.g., age, date of birth, gender, race/ethnicity, and insurance type) will be obtained from the patient’s electronic medical record, and verified via self-report. Demographic variables will likely be used as covariates in analyses. Results of physical examinations, particularly urological and gynecological history as well as urinary symptoms, will be used to determine inclusion criteria. History and diagnoses of serious illness that would preclude study participation will be extracted to determine exclusion criteria (see section 3.2 above). In addition, substance and alcohol use history and diagnoses will be accessed through Epic to establish the exclusion criterion of substance use disorder. Lastly, mental health history and diagnoses will be pulled from Epic for inclusion/exclusion criteria, and to provide background information for therapists.

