### 8.3 Measures

Participants will be asked to complete questionnaires at baseline, mid-treatment (after 6 sessions), posttreatment (after 12 sessions), at a 3-month follow-up, and at a 6-month follow-up. Baseline, mid-treatment, and posttreatment assessments will be completed on tablets with a link from REDcap, though participants will have the option to

respond on paper forms. Both follow-up assessments will be carried out online with a link sent via email. The primary outcome tool for this study will be the six-item Urinary Distress Inventory (UDI-6), which is a subscale of the Pelvic Floor Distress Inventory (PFDI), as measure of urinary symptoms. We will also measure anxiety using a short form from the NIH Patient Reported Outcomes Measurement Information System (PROMIS), which has been shown to be reliable and valid; this form is brief and easy to complete. Secondary measures include the PROMIS profile (depression, fatigue, pain, physical function, sleep disturbance, and social roles), trauma history assessed with the PTSD Checklist for DSM-5 with Life Events Checklist (PCL-5), the Mini-IPIP, a 20-item short form of the International Personality Item Pool measure of the Big Five personality traits, the Ruminative Responses Scale (RRS) short form, and the Patient Global Impression of Improvement (PGI-I) – a one item self-report assessment of improvement of urinary symptoms. In addition, at both follow-up assessments, participants will be asked whether they have received any treatment outside of the study for their urinary symptoms and/or their anxiety. Any treatment participants receive outside of the study will be tracked in this manner and included in data analyses.

Table 2. Timing of Assessments

Measure	Estimated Completion Time	Baseline	Session 6	Session 12	3 Month Post-Treatment Follow-up	6 Month Post-Treatment Follow-up
Medical history and physical exam	0 (part of regular medical visit and extracted from EMR)	X				
Demographic questionnaire	1 min	X				
Single Item Literacy Screener (SILS)	< 1 min	X				
Brief Medication Questionnaire (BMQ) 	3-5 min	X			X	X
Primary outcome 1: PROMIS Anxiety subscale of profile (4 of 29 items below)	See below for entire profile	X	X	X	X	X
Primary outcome 2: Urinary symptoms using the Urinary Distress Inventory (UDI-6) of the Pelvic Floor Distress Inventory (PFDI)	1-3 min	X	X	X	X	X

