### 8.5 Analysis Plan

**Primary analyses.** We will create hierarchical linear models (HLM) to test the primary hypotheses of the study. One model will determine the effect of type of therapy on anxiety. A separate model will determine the effect of type of therapy on urinary symptoms. The dependent variables for these models will be the UDI-6 subscale of the PFDI-20 and anxiety as measured by the anxiety subscale of the PROMIS Profile-29. The structure of the HLM model is shown below. Note that these models create a response profile for each person across all time points as described in the protocol.

#### Level 1

$$Y = P_0 + P_1(T_2) + P_2(T_3) + P_3(T_4) + P_4(T_5) + E$$

#### Level 2

$$P_0 = B_{00} + B_{01}(\text{Condition})$$

$$P_1 = B_{10} + B_{11}(\text{Condition}) + R_1$$

$$P_2 = B_{20} + B_{21}(\text{Condition}) + R_2$$

$$P_3 = B_{30} + B_{31}(\text{Condition}) + R_3$$

$$P_4 = B_{40} + B_{41}(\text{Condition}) + R_4$$

The dummy variables P1-P4 are dummy codes for the five time points. These will allow us to determine the degree of change from baseline. Each of the "P" coefficients is influenced by Level-2 variables. T2 - T5 are dummy variables of the time differences from baseline. E, R1-R4 represent error terms in the model. Condition will be dummy coded (UP-CBT = 1, Supportive Therapy = 0).

**Testing Key endpoints.** We have two primary endpoints and therefore we will have two models. For both anxiety (PROMIS T score) and urinary symptoms (UDI-6), the full model (see above) will be compared to a reduced model with all of the terms involving condition removed (i.e., B01, B11, B21, B31, and B41). If this comparison is significant ( $p < .05$ ), then we will test individual parameters at a Type I error rate of alpha = .05 (two-tailed). Note, these tests will only be carried out if the full-reduced model comparison is

significant. The key prediction for anxiety is that parameters B21, B31, and B41 (representing the effect of UP-CBT at post-treatment and beyond) will be significant and negative (representing fewer symptoms). The key prediction for urinary symptoms is that parameters B21, B31, and B41 (representing the effect of UP-CBT at post-treatment and beyond) will be significant and negative (representing fewer symptoms).

**Missing data.** All participants with baseline data will be included in the modeling using an intent-to-treat approach. The HLM approach described above can accommodate cases with missing follow-up data.

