**Mediation analysis.** We will also carry out mediation analysis in Mplus using bias-correct bootstrapped 95% confidence intervals. We will hypothesize that these confidence intervals will not contain zero for the following mediated effects:

Condition → Mid-treatment anxiety → Post-treatment urinary symptoms

Condition → Post-treatment anxiety → 3-month urinary symptoms

Condition → 3-month anxiety → 6-month urinary symptoms

In addition to testing statistical significance, our hypothesis is directional. Condition (i.e., receiving UP-CBT) should lead to lower anxiety, in turn leading to lower urinary symptoms.

**Exploratory analyses.** Although our primary focus is anxiety and urinary symptoms, we will conduct HLM analyses on each scale of the PROMIS Profile (depression, fatigue, sleep, pain interference, pain, social function) and other subscales of the PFDI (total score, colorectal symptoms, pelvic organ prolapse symptoms). These analyses will be clearly marked as exploratory in all write-ups. We will also create a prediction model of treatment response (i.e., trajectory of symptoms) based on baseline characteristics. These will also be clearly marked as exploratory in all study write-ups.

Table 3. Project Timeline

	Months 1-2	Months 3-4	Months 5-6	Months 7-8	Months 9-10	Months 11-12	Months 13-14
IRB Approval							
Staff Training							
Recruitment							
Pilot RCT Study							
Follow-up Assessments							
Data Analysis							
Manuscript write-up							

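### The three mediation chains name no baseline anxiety or baseline UDI-6, so a stable association between the two scores can pass for mediation

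*Combined protocol and SAP*

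**What the plan says.** The mediation paragraph of section 8.5 reads "We will also carry out mediation analysis in Mplus using bias-correct bootstrapped 95% confidence intervals". The first chain is "Condition → Mid-treatment anxiety → Post-treatment urinary symptoms". The second runs from post-treatment anxiety to 3-month urinary symptoms, and the third from 3-month anxiety to 6-month urinary symptoms. A mediated effect is claimed when the interval excludes zero, and the paragraph adds "In addition to testing statistical significance, our hypothesis is directional". No equations and no covariates are given.

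Three statements elsewhere come near the point without settling it:

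- Section 8.2: "Demographic variables will likely be used as covariates in analyses". This covers demographics only.
- Section 8.3: "Any treatment participants receive outside of the study will be tracked in this manner and included in data analyses". This covers outside treatment, asked about at the two follow-ups.
- Section 8.5, on the dummy variables of the primary hierarchical model: "These will allow us to determine the degree of change from baseline". That model is separate from the Mplus mediation analysis.

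Both baseline scores will exist. Table 2 in section 8.3 marks the anxiety score, "PROMIS Anxiety subscale of profile (4 of 29 items below", and the UDI-6 at baseline and at all four later assessments.

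**The concern.** A mediated effect is the product of two slopes: condition to anxiety (a), and anxiety to later UDI-6 given condition (b). Random allocation makes a a fair comparison. It does nothing for b, which is an observational slope between women. Measuring anxiety one visit before UDI-6 does not help if the difference between women was there at entry and persists.

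Section 2.2 asserts a strong link between distress and urinary symptoms while saying that cause is unexplored, so a baseline association is plausible on the plan's own account. If UP-CBT also lowers anxiety, a is negative, b is positive for a reason unrelated to treatment, and the product has the predicted sign.

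What is at stake is Aim 3 (section 1.2), which uses these analyses to examine cause, and section 14.0, which counts information on the causal link among the benefits. The mediation paragraph lies outside the analyses that section 8.5 promises to label exploratory, and the full-versus-reduced model test is written only for the hierarchical models. The primary endpoints and the sample size are not affected.

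**Working it through.** **The plan's own figure.** The documents give no figure for mediation. Section 4.0 states more than 98% power for d = 1.5 with 16 women per group, two-sided alpha .05. The noncentrality is 1.5 × √(16/2) = 4.24; with 30 degrees of freedom the two-sample t-test has 98.4% power. The figure reproduces. So does the analysed number: 40 × 0.80 = 32.

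**Inputs.** From the documents: 16 per arm, bias-corrected bootstrap 95% interval, d = 1.5. Assumed: r (correlation of anxiety and UDI-6 at baseline), s (correlation of each later score with its own baseline, within arm), and d = 1.0 and 0.5 as smaller effects on anxiety. The d of 1.5 is a general planning figure and may not hold at mid-treatment.

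**Model (SD units, no effect of anxiety or condition on UDI-6).** With X = 1 for UP-CBT:

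- later anxiety A1 = s·A0 − d·X + √(1−s²)·e1
- later UDI-6 U2 = s·U0 + √(1−s²)·e2
- corr(A0, U0) = r; e1 and e2 independent

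**What the unadjusted analysis estimates.** Within arm, the slope of U2 on A1 is r·s², although the true effect is zero. For r = .5 and s = .7 it is .5 × .49 = .245. The apparent mediated effect is −1.5 × .245 = −.37 SD at d = 1.5, and −0.5 × .245 = −.12 SD at d = 0.5. Given A0 and U0, the slope is zero.

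**How often the interval excludes zero.** Each scenario used 2,000 simulated trials with 1,000 resamples each (Monte Carlo error at most 1.1 points). The indirect effect is a·b by least squares, with condition kept in the UDI-6 equation. Cells show false positives per chain, without / with both baselines in both equations.

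| r, s | d = 1.5 | d = 1.0 | d = 0.5 |
|---|---|---|---|
| 0, .7 | 8.9% / 7.5% | 9.1% / 8.6% | 3.6% / 5.0% |
| .2, .5 | 9.7% / 8.9% | 10.3% / 9.2% | 4.0% / 3.7% |
| .3, .5 | 10.8% / 8.2% | 10.5% / 8.6% | 4.8% / 3.4% |
| .5, .5 | 15.2% / 6.6% | 13.9% / 8.7% | 5.9% / 3.6% |
| .3, .7 | 18.3% / 7.5% | 16.9% / 8.7% | 7.4% / 5.0% |
| .5, .7 | 35.2% / 7.9% | 30.1% / 7.1% | 13.8% / 4.0% |
| .6, .8 | 63.6% / 7.4% | 58.5% / 8.2% | 25.8% / 6.8% |

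A separately programmed simulation at r = .5, s = .7 gave 33.5% / 8.5% at d = 1.5 and 14.4% / 5.0% at d = 0.5. With stability .5 for one score and .7 for the other (r = .5, d = 1.5), the unadjusted rate is about 22%.

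**Direction.** At d = 1.5 the share of false exclusions with the predicted sign is 54% at r = 0, 77% at (.2, .5), 85% at (.3, .5), 94% at (.5, .5), and at least 96% when s is .7 or more and r is above zero.

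**Where adjustment falls short.** If each score is a stable trait measured with error (reliability .5 to .8, trait correlation .5 to .85), the rates at d = 1.5 are 55–96% without and 10–19% with the baselines; at d = 0.5 they are 22–38% and 7–13%. If e1 and e2 are themselves correlated, which is confounding arising after baseline, the adjusted rate at r = .5, s = .7, d = 1.5 is about 40–45% at a residual correlation of .3 and about 83% at .5.

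**The case against.** **The arrows are not equations.** Covariates are often left out of path notation, and nothing says that the models will be unadjusted. True, but no other sentence supplies these two baselines, and leaving the choice until the data are in allows two answers from the same trial.

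**The direct path is also unstated.** The table keeps condition in the UDI-6 equation, the usual form. Without it the rate at d = 1.5, r = .5, s = .7 is lower, 22–27%, against about 9% at r = 0. The size changes; the conclusion does not.

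**The size is not known.** This stands. r and s are assumed, selecting women for both conditions may weaken r, and stability may differ by chain: the scores fall about 6 and 12 weeks after baseline in the first, and about 6 and 9 months in the third. At (.2, .5) and (.3, .5) the rates barely differ from r = 0. Of the 35 points in the (.5, .7) cell, about 9 occur with no association and reflect the bias-corrected interval in a small sample.

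**A false chain would usually sit beside a null UDI-6 result.** Under the simulated null this is right. In one run 37.3% of trials gave a false chain, and 1.1% gave both a false chain in the predicted direction and a significant UDI-6 benefit at that visit, so about 97% of false chains (1 − 1.1/37.3) would lack a supporting treatment effect. That helps a careful reader, but the plan does not make the mediation claim depend on it, and a UDI-6 effect by another route would weaken the safeguard.

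**It is a non-primary analysis in a pilot.** Also true, and it limits the weight of the point.

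**Conclusion.** The concern holds and should be fixed. The omission is plain in the text. Its effect ranges from negligible to large: at d = 1.5, from 10% false positives per chain at (r, s) = (.2, .5) to 64% at (.6, .8), against 9% with no association; at d = 0.5, from 4% to 26%, against 4%. These figures assume 16 analysed women per arm, no true anxiety-to-UDI-6 effect, a direct path for condition, and values of r and s that the documents do not give. When association and stability are moderate or more, the directional hypothesis gives no protection.

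Adding the baselines brings the rate back to about 7–9% at d = 1.5 and 1.0, and 3–7% at d = 0.5, provided that the baseline scores carry the confounding. That is roughly the no-association level, not 5%. It does not turn the chains into proof of cause.

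**What to change.** 1. In section 8.5, write out both equations for each of the three chains, with both baseline scores in each:
   - later anxiety = a0 + a·Condition + a1·baseline anxiety + a2·baseline UDI-6 + error
   - later UDI-6 = b0 + c·Condition + b·later anxiety + b1·baseline anxiety + b2·baseline UDI-6 + error

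   The mediated effect is a·b.
2. State that an interval excluding zero is consistent with a causal chain and does not prove one, because measurement error in the baseline scores and confounding after baseline remain.
3. Optional: add a sensitivity table of the mediated effect over a stated range of residual correlation between the two equations.

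The cost is SAP wording and two degrees of freedom per equation at about 32 women; no new data are needed. With an assumed true anxiety-to-UDI-6 slope of .4 SD, r = 0 and s = .7, power goes from 64% to 57% at d = 1.5 and from 23% to 32% at d = 0.5.

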### **1.2 Specific Aims**

1. To demonstrate that UP-CBT is an effective form of therapy for women with lower urinary tract symptoms.
2. To use baseline characteristics in moderation analyses to determine which women will be most likely to have a good response to therapy.
3. To use mediation analyses to test a possible causal chain of events – Does treatment lead to lower anxiety, which in turn leads to fewer urinary symptoms?

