#### **4.0 Sample Size:**

This study will include up to 40 participants. UP-CBT has been shown to have quite large effects (Cohen's  $d$  values of 1.7 or greater). For this study, we have chosen a slightly more conservative estimate for Cohen's  $d$  of 1.5, which represents 1.5 standard deviations between the treatment effect of UP-CBT versus the control group. Based on a power analysis, we would require 16 women per group, in the data analyzed, to detect a treatment effect with  $> 98\%$  power with a Type I error rate of  $\alpha = .05$ , two-tailed. Study withdrawal is estimated at roughly 20%, leaving an estimated final sample of 32 participants for data analysis (see CONSORT diagram below).

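### If UP-CBT lowers anxiety but anxiety does not drive urinary symptoms, the planned bias-corrected mediation interval excludes zero in about 7–9% of trials rather than 5%

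*Combined protocol and SAP*

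**What the plan says.** Section 1.2 (Specific Aims) sets Aim 3: "To use mediation analyses to test a possible causal chain of events", running from treatment through anxiety to urinary symptoms. The mediation paragraph of section 8.5 fixes the method, to be run in Mplus: "bias-correct bootstrapped 95% confidence intervals". It also fixes the decision rule: "We will hypothesize that these confidence intervals will not contain zero for the following mediated effects". Three lagged paths follow: mid-treatment anxiety to post-treatment symptoms, post-treatment anxiety to 3-month symptoms, and 3-month anxiety to 6-month symptoms. The paragraph adds that "In addition to testing statistical significance, our hypothesis is directional".

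The paragraph gives no number of bootstrap draws, no covariates, no multiplicity adjustment and no main path. Section 8.5 labels the analyses of other scales and the prediction model exploratory. The mediation analysis carries no such label, although section 8.1 calls the trial a pilot.

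On size, section 4.0 says "This study will include up to 40 participants" and, after withdrawal, "leaving an estimated final sample of 32 participants for data analysis". The effect size used there is d = 1.5, without saying which of the two primary outcomes it describes.

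**The concern.** A mediated effect is the product of two paths: a (condition to anxiety) and b (anxiety to urinary symptoms, given condition). The product is zero if either path is zero. The null that matters most for Aim 3 is a real effect on anxiety with b = 0: the therapy works on anxiety, but anxiety is not the route to urinary symptoms. The plan predicts a benefit on anxiety, so this is the rival explanation that the mediation test has to exclude.

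The bias-corrected bootstrap moves its percentile limits according to where the estimate falls in the bootstrap distribution. With few participants this can make the interval exclude zero more often than its nominal level under exactly that null. A false result would be read as evidence for the causal chain, and there are three chances to obtain one.

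**Working it through.** **The plan's own figures.** With 16 per arm and d = 1.5, the noncentrality is 1.5 × √(16/2) = 4.243. The normal approximation gives Φ(4.243 − 1.960) = 98.9%, and the noncentral t gives 98.4%. Section 4.0's claim of more than 98% reproduces, as does 40 × 0.8 = 32. The plan states no error rate for the mediation intervals beyond the nominal 95%.

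**Model.** M = aX + e₁ and Y = bM + e₂, with X the condition, normal errors of SD 1, no direct effect and complete data. Condition is controlled when b is estimated. Each setting used 4,000 trials and 1,000 bootstrap draws.
- Percentile limits: the 2.5% and 97.5% points of the bootstrap products.
- Bias-corrected (BC) limits: the Φ(2z₀ ± 1.96) points, where z₀ = Φ⁻¹(share of bootstrap products below the estimate).
- Joint significance: both a and b significant by t test at two-sided .05.

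The 16 per arm comes from section 4.0. All values of a and b are assumptions; a = 1.5 borrows the plan's d. At a rate of 8.6% the Monte Carlo standard error is √(0.086 × 0.914/4000) = 0.4 points.

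**False exclusion of zero (nominal 5%)**

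| Per arm | a | b | BC | Percentile | Joint |
|---|---|---|---|---|---|
| 16 | 0 | 0 | 0.75% | 0.15% | 0.13% |
| 16 | 0.5 | 0 | 3.9% | 1.7% | 1.4% |
| 16 | 0.8 | 0 | 7.0% | 3.7% | 2.9% |
| 16 | 1.0 | 0 | 8.8% | 4.9% | 4.0% |
| 16 | 1.5 | 0 | 8.6% | 6.4% | 4.4% |
| 16 | 0 | 0.30 | 4.0% | 1.7% | 1.5% |
| 16 | 0 | 0.59 | 7.0% | 4.1% | 3.5% |
| 16 | 0 | 1.0 | 9.0% | 6.9% | 5.2% |
| 20 | 1.5 | 0 | 9.3% | 7.2% | 5.6% |
| 100 | 1.5 | 0 | 5.8% | 5.2% | 4.8% |

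Repeat simulations at 16 per arm with b = 0 agree. BC gave 9.0%, 9.0%, 9.1% and 9.4% at a = 1.5, 8.5% at a = 1.0, and 6.8% and 7.6% at a = 0.8. Percentile gave 6.2% to 6.7% at a = 1.5.

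The joint rule cannot truly exceed 5% in this model, because it requires an exact t test to reject a true null. At a = 1.5 and b = 0 its expected rate is 0.984 × 0.05 = 4.9%. The entries above 5% are within two Monte Carlo standard errors of it.

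**Predicted direction only.** With b = 0 and symmetric errors, false exclusions split evenly by sign: 7.0%/2 = 3.5% and 9.0%/2 = 4.5%, against 2.5%. Direct counts in the single-path model at a = 1.0 and 1.5 ran from 3.8% to 4.6%.

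**Three paths.** Three independent tests at exactly 5% give 1 − 0.95³ = 14.3% for at least one false path. At 6.2% (percentile) the figure is 1 − 0.938³ = 17.5%, and at 9% (BC) it is 1 − 0.91³ = 24.6%. A three-path simulation used 2,500 trials, a = 1.5 at every time point, b = 0 and an assumed within-person correlation of 0.5:

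| | Unadjusted | Baseline-adjusted |
|---|---|---|
| First path, BC | 10.3% | 8.4% |
| First path, BC, predicted direction | 5.7% | 4.2% |
| At least one path, BC | 27% | 23% |
| At least one path, percentile | 20% | 18% |
| At least one path, BC, predicted direction | 14% | 12% |

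**Power with a real path, b = 0.5, 16 per arm (percentile v BC).** At a = 0.8, 43% v 55%. At a = 1.0, 57% v 67%. At a = 1.5, 71% v 77%. The differences are 12, 10 and 6 points.

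**The case against.** The strongest reply is that this is a modest excess, under some nulls only, in a non-primary aim of a small pilot. Neither primary endpoint depends on the mediation analysis. The hypothesis is directional, so an interval on the wrong side would not support Aim 3. The percentile interval also runs above 5% at a = 1.5 and loses power. All of that stands, and it limits the weight of the point. It does not remove it: the directional excess remains, and the mediation analysis is not among those labelled exploratory.

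Three stronger readings are tempting, and neither the documents nor the calculations support them.

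- A reader might infer that the intervals over-reject whenever there is no mediation. They do not: BC is very conservative with both paths zero, and at or below about 4% when the one non-zero path is weak (a = 0.5 or b = 0.30).
- A reader might infer that the plan itself assumes d = 1.5 for anxiety and that this large value drives the problem. Section 4.0 names no outcome, and the BC rate is already about as high at a = 1.0 as at 1.5.
- A reader might blame the bias correction for a chance of about 25% of at least one false path. Most of that is multiplicity, since three tests at a correct 5% already give 14.3%. The figure also needs a large anxiety effect at mid-treatment, whereas section 8.5's key predictions start at post-treatment.

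**Conclusion.** The concern holds in limited form. The nominal 95% is wrong for the null that Aim 3 most needs to reject: the real two-sided error is about 7–9% if the anxiety effect is between 0.8 and 1.5 SD. The excess is largely a small-sample effect, falling to 5.8% at 100 per arm with a = 1.5. The mirror null, no effect on anxiety but a strong anxiety-to-symptom path, behaves similarly.

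These figures assume normal errors, complete data on 32 women and a simple single-mediator model. The plan does not specify its Mplus model or the strength of the anxiety-to-symptom path. The point is worth correcting before analysis because it is cheap to correct, but it has no bearing on the primary comparisons.

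**What to change.** In the mediation paragraph of section 8.5:

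1. Replace the bias-corrected interval with a percentile bootstrap interval and state the number of draws.
2. Claim mediation only if that interval excludes zero in the predicted direction and the condition-to-anxiety and anxiety-to-urinary paths are each significant at two-sided .05. The second condition is needed because the percentile interval alone does not restore 5% at a = 1.5.
3. Keep the bias-corrected interval, if wanted, as a sensitivity analysis.
4. Name one path as the main mediation test, for example post-treatment anxiety to 3-month symptoms, and call the other two supportive. Three unadjusted tests compound the error whichever interval is used.

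The cost is a text change and no new data. Power for a true mediated effect falls by roughly 5 to 12 points from the change of interval (b = 0.5); part of that power came from the excess error. Adding the joint requirement can only hold power level or lower it further, by an amount not computed here.
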